## **4. TREATMENT PLAN**

Patients with advanced and metastatic biliary tract adenocarcinoma (cholangiocarcinoma) who had been treated and failed first-line chemotherapy, ECOG PS 0-1, and adequate liver, kidney and bone marrow function will be treated with regorafenib (160 mg) orally once daily for 21 days on and 7 days off in a 28-day cycle. Tissue specimens collected at diagnosis may be submitted for molecular analyses or other studies.

A maximum of 37 patients will be enrolled.

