Study design	Patients with advanced and metastatic biliary tract adenocarcinoma (cholangiocarcinoma) who had been treated with and failed first-line chemotherapy will be treated with regorafenib (120 mg) orally once daily 21 days (3 weeks) on and 7 days (1 week) off in the 28-day (4-week) cycle.
Type of control	Single arm uncontrolled

Number of subjects	Maximum of 37 patients.
Plan for statistical analysis	
There will be no stratification. OR will be estimated at end of trial with 95% exact binomial confidence intervals. PFS and OS will be estimated by the Kaplan-Meier method, with appropriate 90% confidence intervals. Toxicity events will be tabulated. Change in CA19-9 and CEA will be characterized by their mean changes, with a nonparametric CDF-based 90% confidence interval. The study will have 83% power (using a one-sided test at <math>\alpha=0.10</math>) to reject the null hypothesis (PFS<2.0 months) if the true median PFS is at least 3.5 months.

Schema:

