## 2.2.2 Clinical experience

Two Phase 3 global randomized studies have evaluated the efficacy of regorafenib. The CORRECT (Patients with metastatic colorectal cancer treated with regorafenib or placebo after failure of standard therapy) trial is an international, multicenter, randomized, double-blind, placebo-controlled study with 114 centers in 16 countries. Patients with documented metastatic colorectal cancer and progression during or within 3 months after the last standard therapy were randomized (in a 2:1 ratio; stratified by previous treatment with anti-VEGF therapy, time from metastatic disease diagnosis, and geographical area) to receive oral regorafenib, 160 mg once daily, plus best supportive care (BSC) or placebo plus BSC, with 3 weeks on and 1 week off as a cycle. The primary endpoint was overall survival. From April 30, 2010 to March 22, 2011, there were 1052 patients screened, 760 patients were randomized to receive regorafenib (n=505) or placebo (n=255); 753 patients initiated treatment (regorafenib n=500; placebo n=253). The primary endpoint of overall survival was met at a preplanned interim analysis. Median overall survival was 6.4 months in the regorafenib treatment arm versus 5.0 months in the placebo arm (HR of 0.77; 95% CI 0.64–0.94; one-sided p=0.0052). Treatment-related adverse events occurred in 465 (93%) patients assigned regorafenib and in 154 (61%) of those assigned placebo. The most common adverse events of grade three or higher related to regorafenib were hand-foot skin reaction (83 patients, 17%), fatigue (48, 10%), diarrhea (36, 7%), hypertension (36, 7%), and rash or desquamation (29, 6%).

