### **4.1 Regorafenib Administration**

Treatment will be administered on an outpatient basis. Reported adverse events and potential risks are described in Section 6. Appropriate dose modifications are described in Section 5. No investigational or commercial agents or therapies other than those described below may be administered with the intent to treat the patient's malignancy.

**The starting dose of regorafenib will be 120 mg once daily for the first cycle. However, for those patients who show no regorafenib dose related toxicity after the dose level 120mg/day when at the end of cycle 1 treatment, the dose level may escalate to 160mg/day for the second and subsequent cycles.** Study medication will be administered on a 3 weeks on and 1 week off schedule [3 weeks out of every 4].

At the start three 40-mg regorafenib tablets [unless dose-reduced, Section 6] should be taken in the morning with approximately 8 fluid ounces (240 mL) of water after a low-fat (<30% fat) breakfast for cycle 1. The number of regorafenib tablets of subsequent cycles should be taken based on the AE profile of the previous cycles.

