### 5. DOSING DELAYS/DOSE MODIFICATIONS

Doses will be delayed or reduced for clinically significant hematologic and non-hematologic toxicities that are related to protocol therapy according to the guidelines shown in the Dose Delays/Dose Modifications table that follows. Dose modifications will follow predefined dose levels. Dose adjustments for hematologic toxicity are based on the blood counts obtained in preparation for the day of treatment.

Modifications of regorafenib will follow the following predefined dose levels:		
#Dose level +1	160 mg, daily, orally	Four 40-mg tablets of regorafenib
Dose level 0 (Standard starting dose)	120 mg, daily, orally	Three 40-mg tablets of regorafenib
Dose level -1	80 mg, daily, orally	Two 40-mg tablets of regorafenib
Dose level -2	40 mg, daily, orally	One 40-mg tablet of regorafenib

#Only for those patients with no regorafenib dose related toxicity after the 1st cycle dose level of regorafenib 120mg/day, the dose level may escalate to 160mg/day for the second and subsequent

cycles.

If a patient experiences more than one toxicity, dose reduction should be according to the toxicity with the highest grade.

In the case of two or more toxicities of the same grade, the investigator may dose reduce according to that deemed most causally related to study treatment.

The following tables outline dose adjustments for toxicities related to study drug except hand-foot skin reaction, hypertension, and liver function test abnormalities.

**Table 5-1: Recommended dose modification for toxicities except hand-foot-skin reaction, hypertension and ALT/ST/bilirubin**

NCI-CTCAE v4.0 a	Dose Interruption	Dose Modification b	Dose for Subsequent Cycles
Grade 0-2	Treat on time	No change	No change
Grade 3	Delay until $\leq$ Grade 2 c,d	Reduce by 1 dose level	If toxicity remains $<$ Grade 2, dose re-escalation can be considered at the discretion of the treating (Sub-) investigator. If dose is re-escalated and toxicity ( $\geq$ Grade 3) recurs, institute permanent dose reduction.
Grade 4	Delay until $\leq$ Grade 2 c	Reduce by 2 dose levels. Permanent discontinuation can be considered at the treating (Sub-)investigator's discretion.	

a. NCI-CTCAE = National Cancer Institute - Common Terminology Criteria for Adverse Events, version 4.0

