**Table 5.3 Recommended dose modification for hand-foot-skin reactiona**

Grade of event (NCI-CTCAE v4.0)	Occurrence	Suggested Dose Modification
Grade 1	Any	Maintain dose level and immediately institute supportive measures for symptomatic relief
Grade 2	1 st occurrence	Consider decreasing dose by one dose level and immediately institute supportive measures. If no improvement, interrupt therapy for a minimum of 7 days, until toxicity resolves to Grade 0-1 b,c
	No improvement within 7 days or 2 nd occurrence	Interrupt therapy until toxicity resolves to Grade 0-1. c When resuming treatment, treat at reduced dose level. b
	3 rd occurrence	Interrupt therapy until toxicity resolves to Grade 0-1. c When resuming treatment, decrease dose by one dose level. b,d
	4 th occurrence	Discontinue therapy

Grade 3	1 st occurrence	Institute supportive measures immediately. Interrupt therapy for a minimum of 7 days until toxicity resolves to Grade 0-1. c When resuming treatment, decrease dose by one dose level. b,d
	2 nd occurrence	Institute supportive measures immediately. Interrupt therapy for a minimum of 7 days until toxicity resolves to Grade 0-1. c When resuming treatment, decrease dose by one additional dose level b,d
	3 rd occurrence	Discontinue treatment permanently.

a. More conservative management is allowed if judged medically appropriate by the investigator.  
 b. If toxicity returns to Grade 0-1 after dose reduction, dose re-escalation is permitted at the discretion of the investigator if subject has completed one cycle at reduced dose without recurrence of event.  
 c. If there is no recovery after a 4-week delay, treatment with regorafenib will be discontinued permanently.  
 d. Subjects requiring > 2 dose reductions should go off protocol therapy.  
 The maximum daily dose is 160 mg.

Prior to starting regorafenib and at first occurrence of HFSR, independent of grade, prompt institutional supportive measures such as topical emollients, low potency steroids, or non-urea-containing creams should be administered. Patients should be educated on prevention/management strategies for HFSR.

Recommended prevention/management strategies for skin toxicities consistent with HFSR are summarized below:

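### Section 4 gives 160 mg daily as the treatment dose for all patients, but Section 4.1, the dose-level table and the synopsis say 120 mg; the Section 4 figure should be corrected.

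*Combined protocol and SAP*

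**What the plan says.** The protocol states the regorafenib dose in several operative places.

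- **Section 4, opening paragraph.** Patients "will be treated with regorafenib (160 mg) orally once daily for 21 days on and 7 days off in a 28-day cycle". The sentence covers every eligible patient and mentions neither the cycle nor escalation nor toxicity.
- **Section 4.1 (bold).** "The starting dose of regorafenib will be 120 mg once daily for the first cycle". For patients with no dose-related toxicity at the end of cycle 1, "the dose level may escalate to 160mg/day for the second and subsequent cycles". The same section specifies three 40-mg tablets at the start.
- **Section 5, dose-level table.** The row labelled "Dose level 0 (Standard starting dose)" is 120 mg, three tablets. The 160 mg row is level +1, and its footnote restricts it: "Only for those patients with no regorafenib dose related toxicity after the" first cycle at 120 mg.
- **Synopsis, Study design.** In a sentence built almost like the one in Section 4, patients "will be treated with regorafenib (120 mg) orally once daily".
- **Table 5.3, footnotes.** "The maximum daily dose is 160 mg".

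**The concern.** Section 4 is the Treatment Plan, where site staff would look for the dose, and its first sentence gives a figure that the rest of the protocol contradicts. Nothing in the text reconciles the two.

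The difference affects safety. The protocol makes 160 mg conditional on a first cycle at 120 mg without dose-related toxicity. A patient started at 160 mg would never pass through that check and would begin one dose level too high. The conflict also leaves two different doses against which a monitor could judge compliance or a deviation.

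**Working it through.** This is a consistency check. No sample-size, power or alpha calculation enters into it.

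**Step 1: set the statements side by side.**

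| Place | Daily dose | Condition |
|---|---|---|
| Section 4, opening paragraph | 160 mg | none |
| Section 4.1 | 120 mg in cycle 1 | 160 mg optional from cycle 2 if no dose-related toxicity |
| Section 5, dose-level table | 120 mg (level 0) | 160 mg is level +1, with the same restriction |
| Synopsis, Study design | 120 mg | none stated |

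**Step 2: check the tablet count.** Section 4.1 and level 0 both specify three 40-mg tablets: 3 × 40 mg = 120 mg. A dose of 160 mg needs 4 × 40 mg, which the table assigns to level +1. The tablet instructions therefore support 120 mg as the start.

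**Step 3: see whether Section 4 can be read another way.**

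- *As the escalated dose.* Escalation is optional and conditional, while Section 4 says what all patients will receive.
- *As the maximum.* The maximum is stated separately in the footnotes to Table 5.3, and Section 4 does not present its figure as a ceiling.
- *As the treatment dose.* This is the natural reading, and the near-parallel synopsis sentence gives 120 mg in the same position.

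Only the third reading fits the wording, and under it the number is wrong.

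**Step 4: size of the discrepancy if Section 4 were followed in cycle 1.**

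- Daily dose: 160 / 120 = 1.33, or 33% more.
- Section 4 over 21 dosing days: 160 × 21 = 3,360 mg, and 3,360 / 40 = 84 tablets.
- Section 4.1 over 21 dosing days: 120 × 21 = 2,520 mg, and 2,520 / 40 = 63 tablets.
- Difference: 3,360 − 2,520 = 840 mg, and 84 − 63 = 21 tablets.
- Share of the 160 mg maximum daily dose: 160 / 160 = 100% instead of 120 / 160 = 75%.

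**A smaller query, in Table 5-1.** For Grade 3 events, the cell on later cycles appears to allow re-escalation when toxicity stays below Grade 2. The note under the table allows it at Grade 2 or lower. The two differ only at exactly Grade 2. The cell depends on one symbol in a machine-read table, which may be a less-than-or-equal sign that was lost. The restart rule in the same row uses Grade 2 or lower, which agrees with the note. This needs a look at the source document and is not a finding in itself.

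**The case against.** The best case for leaving the matter alone is that the controlling text is clear. The Section 4 paragraph is a short overview that also covers eligibility, tissue and enrolment. The dosing instruction comes immediately afterwards in bold, with the escalation rule and a tablet count, and the dose-level table repeats it. Anyone dispensing cycle 1 needs a tablet count, and the protocol's instruction for the start is three.

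Nor is 160 mg an alien dose here. It is the protocol's maximum and is permitted from cycle 2. It is also the dose in both Phase 3 trials described in Section 2.2.2; in the colorectal trial, for example, patients were randomised "to receive oral regorafenib, 160 mg once daily, plus best supportive care (BSC)." The 33% and 840 mg figures describe a hypothetical patient and are not evidence of harm.

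All of this stands, and it limits the weight of the point. It does not make the Section 4 figure correct. That the right dose is easy to find makes the correction easy; it is no reason to keep a contradictory dose in the same section.

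Two narrower objections are also fair. The synopsis gives 120 mg as the treatment dose without calling it a starting dose or mentioning escalation, so it supports 120 mg over 160 mg but is itself incomplete. And the Table 5-1 query is a separate matter of little consequence: re-escalation is at the investigator's discretion, and a recurrence at Grade 3 or above leads to permanent reduction. The main point does not rest on it.

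**Conclusion.** The point holds and is minor. The 160 mg in the opening paragraph of Section 4 is an error in current operative text, and the intended starting dose is 120 mg.

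The potential size is one dose level per patient in cycle 1, and the protocol maximum would not be exceeded. This assumes that someone follows Section 4 literally and ignores Section 4.1; nothing in the documents shows that anyone was dosed this way. The planned 37 patients, the one-sided alpha of 0.10 and the stated 83% power do not depend on the wording. Confidence is high for the dose contradiction. The Table 5-1 symbol remains an open query, and the number of patients it could affect cannot be computed from the documents.

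**What to change.** 1. In Section 4, replace the 160 mg statement with: 120 mg once daily in cycle 1, with optional escalation to 160 mg from cycle 2 for patients with no regorafenib dose-related toxicity. The 21-days-on, 7-days-off schedule stays as it is.
2. While editing, consider adding the same escalation clause to the synopsis so that it matches Section 4.1 in full.
3. Check the re-escalation symbol in Table 5-1 against the source document. If it really is a strict less-than sign, state one threshold in both the cell and the note. Which threshold to use is for the sponsor to decide.

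The cost is one sentence in Section 4, an optional clause in the synopsis and, if the symbol is confirmed, one edit to Table 5-1 or its note. No patients, visits or procedures are added.

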### **4.1 Regorafenib Administration**

Treatment will be administered on an outpatient basis. Reported adverse events and potential risks are described in Section 6. Appropriate dose modifications are described in Section 5. No investigational or commercial agents or therapies other than those described below may be administered with the intent to treat the patient's malignancy.

**The starting dose of regorafenib will be 120 mg once daily for the first cycle. However, for those patients who show no regorafenib dose related toxicity after the dose level 120mg/day when at the end of cycle 1 treatment, the dose level may escalate to 160mg/day for the second and subsequent cycles.** Study medication will be administered on a 3 weeks on and 1 week off schedule [3 weeks out of every 4].

At the start three 40-mg regorafenib tablets [unless dose-reduced, Section 6] should be taken in the morning with approximately 8 fluid ounces (240 mL) of water after a low-fat (<30% fat) breakfast for cycle 1. The number of regorafenib tablets of subsequent cycles should be taken based on the AE profile of the previous cycles.

### **4.2 Examples of a low fat breakfast**

Two slices of white toast with 1 tablespoon of low-fat margarine and 1 tablespoon of jelly and 8 ounces of skim milk. (Approximately 319 calories and 8.2 grams of fat)

One cup of cereal (i.e., Special K), 8 ounces of skimmed milk, one piece of toast with jam (no butter or marmalade), apple juice, and one cup of coffee or tea (2 g fat, 17 g protein, 93 g of carbohydrate, 520 calories).

The patient will be requested to maintain a medication diary of each dose of medication. The medication diary will be returned to clinic staff at the end of each course

### **4.3 Prior and concomitant therapy**

All medication that is considered necessary for the subject's welfare, and which is not expected to interfere with the evaluation of the study treatment, may be given at the discretion of the investigator. All medications (including contrast media) taken within 2 weeks prior to the start of the study and during the study must be recorded in the subject's source documentation and in the research data base (including start/stop dates, dose frequency, route of administration, and indication). Specific caution should be taken when considering or administering a concomitant medication that is metabolized by the cytochrome enzymes CYP2C8, CYP2B6 and CYP2C9. Such concomitant medication should be avoided, if possible.

Co-administration of a strong CYP3A4 inducer (rifampin) with a single 160 mg dose of regorafenib decreased the mean exposure of regorafenib, increased the mean exposure of the active metabolite M-5, and resulted in no change in the mean exposure of the active metabolite M-2. Avoid concomitant use of regorafenib with strong CYP3A4 inducers (e.g. rifampin, phenytoin, carbamazepine, phenobarbital, and St. John's Wort).

Co administration of a strongCYP3A4 inhibitor (ketoconazole) with a single 160 mg dose of Stivarga increased the mean exposure of regorafenib and decreased the mean exposure of the active metabolites M-2 and M-5. Avoid concomitant use of regorafenibwith strong inhibitors of CYP3A4 activity (e.g. clarithromycin, grapefruit juice, grapefruits, Seville oranges, itraconazole, ketoconazole, nefazadone, posaconazole, telithromycin, and voriconazole).

Permitted concomitant therapies include:

- Standard therapies for concurrent medical conditions.
- Supportive care for any underlying illness.
- Palliative radiation therapy is allowed if the target lesion(s) are not included within the radiation field and no more than 10% of the bone marrow is irradiated.
- Granulocyte colony-stimulating factor (G-CSF) and other hematopoietic growth factors may be used in the management of acute toxicity, such as febrile neutropenia, when clinically indicated or at the investigator's discretion. However, they may not be substituted for a required dose reduction. Subjects are permitted to take chronic erythropoietin.
- Treatment with nonconventional therapies (such as acupuncture), and vitamin/mineral supplements are permitted provided that they are reviewed by the investigator and are deemed acceptable.
- Bisphosphonates
- Subjects who are therapeutically treated with an agent such as warfarin or heparin will be allowed to participate provided that their medication dose and INR/PTT are stable. Close monitoring (day5 of cycle 1 and day 1 of each cycle) is mandatory. If either of these values is above the therapeutic range, the doses should be modified and the assessments should be repeated weekly until they are stable.

The following are not permitted:

- Other investigational treatment during or within 28 days before starting study treatment

- Systemic antitumor therapy, including cytotoxic therapy, signal transduction inhibitors, immunotherapy, and hormonal therapy
- Bone marrow transplant or stem cell rescue
- Subjects taking narrow therapeutic index medications should be monitored proactively (e.g. warfarin, phenytoin, quinidine, carbamazepine, Phenobarbital, cyclosporine, and digoxin). Warfarin is metabolized by the cytochrome enzyme CYP2C9 and its levels may be especially affected by regorafenib
- Use of any herbal remedy (e.g. St. John's wort [Hypericum perforatum])

#### 4.4 Treatment compliance

An adequate record of receipt, distribution, and return of all study drugs must be kept in the form of a Drug Accountability Form.

Subject compliance with the treatment and protocol includes willingness to comply with all aspects of the protocol, and to have blood collected for all safety evaluations. At the discretion of the principal investigator, a patient may be discontinued from the trial for non-compliance with follow-up visits or study drug.

#### 4.5 Duration of Follow Up

Patients will be followed every 3 months (+/- 4 weeks) until death or study closure. Follow-up will be by either direct contact or medical record review.

### 5. DOSING DELAYS/DOSE MODIFICATIONS

Doses will be delayed or reduced for clinically significant hematologic and non-hematologic toxicities that are related to protocol therapy according to the guidelines shown in the Dose Delays/Dose Modifications table that follows. Dose modifications will follow predefined dose levels. Dose adjustments for hematologic toxicity are based on the blood counts obtained in preparation for the day of treatment.

Modifications of regorafenib will follow the following predefined dose levels:		
#Dose level +1	160 mg, daily, orally	Four 40-mg tablets of regorafenib
Dose level 0 (Standard starting dose)	120 mg, daily, orally	Three 40-mg tablets of regorafenib
Dose level -1	80 mg, daily, orally	Two 40-mg tablets of regorafenib
Dose level -2	40 mg, daily, orally	One 40-mg tablet of regorafenib

#Only for those patients with no regorafenib dose related toxicity after the 1st cycle dose level of regorafenib 120mg/day, the dose level may escalate to 160mg/day for the second and subsequent

cycles.

If a patient experiences more than one toxicity, dose reduction should be according to the toxicity with the highest grade.

In the case of two or more toxicities of the same grade, the investigator may dose reduce according to that deemed most causally related to study treatment.

The following tables outline dose adjustments for toxicities related to study drug except hand-foot skin reaction, hypertension, and liver function test abnormalities.

**Table 5-1: Recommended dose modification for toxicities except hand-foot-skin reaction, hypertension and ALT/ST/bilirubin**

NCI-CTCAE v4.0 a	Dose Interruption	Dose Modification b	Dose for Subsequent Cycles
Grade 0-2	Treat on time	No change	No change
Grade 3	Delay until $\leq$ Grade 2 c,d	Reduce by 1 dose level	If toxicity remains $<$ Grade 2, dose re-escalation can be considered at the discretion of the treating (Sub-) investigator. If dose is re-escalated and toxicity ( $\geq$ Grade 3) recurs, institute permanent dose reduction.
Grade 4	Delay until $\leq$ Grade 2 c	Reduce by 2 dose levels. Permanent discontinuation can be considered at the treating (Sub-)investigator's discretion.	

a. NCI-CTCAE = National Cancer Institute - Common Terminology Criteria for Adverse Events, version 4.0

b. Excludes alopecia, non-refractory nausea/vomiting, non-refractory hypersensitivity and nonclinical and asymptomatic laboratory abnormalities.

c. If no recovery after a 4 week delay\*, treatment should be permanently discontinued unless subject is deriving clinical benefit.

d. For G3 AE for level of phosphate and magnesium only patient may continue tx at MD discretion. MD will provide appropriate intervention, as needed.

Note: these dose modifications are for the current cycle based on the grade of toxicity, there will not be re-escalating in the same cycle. However, 're-escalation' in subsequent cycles is possible, if toxicity remains grade 2 or less, and will be 'at the discretion of the treating (Sub-) investigator.

